## **12.0 Participant Information**

### **12.1 Subject Population:**

Active Duty members and DoD beneficiaries, 18 years or older, meeting the inclusion/exclusion criteria will be recruited.

### **12.2 Age Range:**

Check all the boxes that apply. If the age range of potential subjects (specimens, records) does not match the range(s) selected, please specify in the text box.

- 0-17
- 18-24
- 25-34
- 35-44
- 45-54
- 55-64
- 65-74
- 75+

### **12.3 Gender:**

- Male
- Female
- Other

### **12.4 Special categories, check all that apply**

- Minors /Children
- Students
- Employees - Civilian
- Employees - Contractor
- Resident/trainee
- Cadets /Midshipmen
- Active Duty Military Personnel

- Wounded Warriors
- Economically Disadvantaged Persons
- Educationally Disadvantaged Persons
- Physically Challenged (Physical challenges include visual and/or auditory impairment)
- Persons with Impaired Decisional Capacity
- Prisoners
- Pregnant Women, Fetuses, and Neonates
- Non-English Speakers
- International Research involving Foreign Nationals - Headquarters Review is necessary

## 12.5 Inclusion Criteria:

Order Number	Criteria
1	
Inclusion Criteria: (adapted)
 
 
-Active duty and DoD Beneficiaries aged 18 years or older
 
-Pain
 

## 12.6 Exclusion Criteria:

Order Number	Criteria
1	
Exclusion Criteria: (adapted)
 
 
-Contra-indication to needle use including known bleeding disorder and psychogenic issues related to needle use (e.g., needle-phobia)
 
-Allergy to metal or neutropenia
 
-Women who are pregnant, may be pregnant, or attempting to become pregnant
 

## 13.0 Recruitment and Consent

### 13.1 Please describe the recruitment process, including how subjects will be identified and selected for the study.

All potentially eligible patients will be offered an opportunity to participate. Primary Care Manager (PCM) referrals, with the patient's oral or written authorization, and posted advertisements will be utilized for recruiting subjects to the study. Some patients may be patients of the PI or AI; however, they will have another study staff recruit their patients to prevent any misconception of coercion or undue influence. When a potential subject is identified by the treating PCM, the patient will either be provided a contact number to the Research Staff, the Research Staff will be given the potential subjects' contact information by the PCM, or the Research Staff will speak with the patients directly.

### 13.2 Compensation for Participation:

Subjects will not be paid for their participation.

### 13.3

**Please describe the pre-screening process. If no pre-screening, enter Not Applicable in the text editor**

Pre-Eligibility review: Subjects who responded to advertisements or have given their permission to be contacted will be approached by a study staff member to discuss the subjects' interest in the research study and to receive a pre-eligibility screening for study participation. The attached "Pre-Eligibility Review Script" will be used and response will be recorded. If the subject is interested in participating in the study, the study staff member will schedule a screening visit while the subject waits on the phone or in-person, in order to confirm the schedule appointment with the subject. Following the pre-screening procedure, the script will be shredded.

**13.4 Consent Process:**

**Revised Common Rule, Section 219.116: General requirements for informed consent, whether written or oral, are set forth in this paragraph and apply to consent obtained in accordance with the requirements set forth in paragraphs (b) through (d) of this section. Broad consent may be obtained in lieu of informed consent obtained in accordance with paragraphs (b) and (c) of this section only with respect to the storage, maintenance, and secondary research uses of identifiable private information and identifiable biospecimens.**

Are you requesting a waiver or alteration of informed consent?

Yes  No

Please explain the consent process:

Informed Consent and HIPAA authorization will be sought in advance of any screening and study-related procedures from each prospective study subject and appropriately documented in accordance with 32 CFR 219.117. Potential candidates will be notified about the study either through posted advertisements or by their healthcare provider and will be given the opportunity to consent by one of the referred study coordinators. The study coordinator will provide a written copy of the Informed Consent Document (ICD). The subject may decline to consent without prejudice. At the subjects' discretion, they may take the ICD home to discuss further with family members or another physician prior to making a decision. If they decide they are interested in participating in the study, they can contact the research department. If the subject consents, a copy of the signed ICD and HIPAA Authorization Document will be given to the subject. No vulnerable populations are included in this research study. Subjects who cannot provide Informed Consent will not be allowed to participate. No Legally Authorized Representatives (LAR) will be utilized. Each subject will be asked to place their de-identified research data into the "Nellis Acupuncture Data Repository" (FWH20140048H) for future research. If the subject does not give their authorization, then the de-identified research data will be destroyed no later than at 3 years after closure of the study. HIPAA forms will be maintained in hardcopy format for a minimum of 6 years.

**13.5 DoDI 3216.02 requires an ombudsman to be present during recruitment briefings when research involves greater than minimal risk and recruitment of Service members occurs in a group setting. If applicable, you may nominate an individual to serve as the ombudsman.**

N/A  
 Propose ombudsman

**13.6 Withdrawal from Study Participation:**

Explain the process for withdrawal and specify whether or not the subjects will be given the opportunity to withdraw their data their data/specimens in the event they wish to withdraw from the study

If a participant first agrees to participate and then changes their mind, they are free to withdraw consent and discontinue participation at any time. Their decision will not affect their ability to receive medical care and will not be penalized or lose any benefits to which they would otherwise be entitled. There are no risks from withdrawing. They will be advised in the Informed Consent process that if they decide to withdraw from the study early, we will ask them to discuss their decision with the study staff. The researcher may withdraw them from the study prior to the study's end without their consent for one or more of the following reasons: Failure to follow the instructions of the researchers and study staff. The

researcher decides that continuing their participation is not in their best interests. The study is cancelled. Other administrative reasons. Unanticipated circumstances. They become Pregnant. If they lose their status as a military health care beneficiary, they can no longer be included in the study.

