##### **Acupuncture Needles:**

Auricular semi-permanent (ASP gold) needles: will be remain in your ears for 2-8 days and allowed to fall out on their own.

Intradermal (long) needles using J-type No. 1 (.16) x 15mm: remain in place for 15-30 minutes and are removed by a member of the study staff.

Pylonex needles (Pylonex Pink 1.5mm (0.2 x 1.5mm)): that will be remain in your ears for 2-21 days and allowed to fall out on their own.

This study received DoD Survey License Exemption (#14)-Exempt #0033.

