# 11.0

## Statistical/Data Analysis Plan

### 11.1 Statistical Considerations:

List the statistical methods to be used to address the primary and secondary objectives, specific aims, and/or research hypotheses. Explain how missing data and outliers will be handled in the analysis. The analysis plan should be consistent with the study objectives. Include any sub-group analyses (e.g., gender or age group). Specify statistical methods and variables for each analysis. Describe how confounding variables will be controlled in the data analysis

**Outcome Measures:** There are two outcome measures. The effectiveness outcome measure is the Defense and Veterans Pain Rating Scale (DVPRS). The DVPRS [1,2] consists of an 11-point numerical rating scale with 0 indicating no pain and 10 indicating severe pain. It has been confirmed for reliability and validity in measuring both acute and chronic pain, and is currently the standard for pain measurement throughout DoD and VA health systems. The DVPRS demonstrates linear scale qualities allowing parametric methods to be used. There will be four repeated measurements of the DVPRS: pre-acupuncture, post-acupuncture, 24 hours and one week post-therapy. The needle tolerance outcome will be measured using an in-house developed questionnaire. It employs 5-point ordinal scales to evaluate 12 post-therapy experiences or perception encompassing adverse outcomes, inconveniences, and satisfaction. There will be three repeated measurements: post-acupuncture, 24 hours and 1 week post-therapy.

**Missing Data and Outliers:** Outliers will be checked for clerical error. If improperly recorded, the data will be corrected, and, if found to be properly recorded, will be retained. Medians, means and ranges will be calculated and assessed to accommodate extreme observations. Subjects with missing data will be excluded from analysis and the estimated sample size seen below adjusted for this eventuality. Furthermore, an analysis of sample characteristics of retained and dropped subjects will be performed to determine whether bias has been introduced due to exclusion.

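### The open withdrawal ground in 13.6, combined with complete-case analysis in 11.1, could drop subjects who take a needle out early because of discomfort, along with tolerance answers already given

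*Combined protocol and SAP*

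**What the plan says.** **Withdrawal (13.6).** "The researcher may withdraw them from the study prior to the study's end without their consent", and the first reason listed is "Failure to follow the instructions of the researchers and study staff". No act is named as a breach, and nothing is said about collecting questionnaires after such a withdrawal. The clause applies to every arm.

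**Needle wear (10.1, Acupuncture Needles).** ASP needles "will be remain in your ears for 2-8 days and allowed to fall out on their own". Pyonex needles are described as ones "that will be remain in your ears for 2-21 days and allowed to fall out on their own". Long needles "remain in place for 15-30 minutes and are removed by a member of the study staff".

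**Missing data (11.1).** "Subjects with missing data will be excluded from analysis". The only safeguard is that "an analysis of sample characteristics of retained and dropped subjects will be performed to determine whether bias has been introduced due to exclusion".

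**Tolerance (11.1 and 10.1).** Tolerance is one of the two outcome measures. It is scored on a questionnaire designed "to evaluate 12 post-therapy experiences or perception encompassing adverse outcomes, inconveniences, and satisfaction", given 10-15 minutes, 24 hours and 7 days after treatment.

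**Blinding and size.** The Aim in 9.3 describes the study as unblinded. Section 9.4 recruits 13 subjects per group in order to analyse at least 10.

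**The concern.** Taking a needle out because it hurts is information about tolerance. The protocol expects discomfort: 14.1 lists pain among the likely risks, and 9.6 says that painful ASP needles keep patients from returning. Yet the available text does not say how early removal is to be recorded or analysed.

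If a staff member who knows the needle type treats removal as non-compliance and ends participation, the remaining contacts are empty and 11.1 then drops the whole subject. An exclusion after randomization would then depend on the outcome being compared. The opportunity also differs by arm, because only two of the three needle types go home with the subject. At stake is the comparison of ASP and Pyonex with long needles on tolerance, which both hypotheses in 9.3 cover.

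**Working it through.** **Step 1. What the text supplies and what has to be assumed.**

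| Link | In the text | Assumed |
|---|---|---|
| Subject removes a needle at home | Possible with ASP (2-8 days) and Pyonex (2-21 days) | How often, and why |
| Removal is judged a failure to follow instructions | 13.6 leaves the term undefined | That staff read the wear description as an instruction |
| Subject is withdrawn | Researcher may do so | That the option is used |
| Questionnaires are missing | 24-hour and 7-day contacts would follow the withdrawal | That contact stops |
| Subject leaves the analysis | 11.1, as written | Nothing further |

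The last link needs no assumption. The rule excludes the subject and not merely the missing record, so a subject withdrawn on day 2 also loses the 10-15 minute and 24-hour answers already given. The route matters only up to the 7-day contact (7 plus or minus 2 days); a Pyonex needle removed after that contact costs no data.

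**Step 2. The plan's own allowance.** From 9.3, 9.4 and 11.2: 30 x 1.30 = 39 recruited; 39/3 = 13 per arm; 13 - 10 = 3 losses per arm; 3/13 = 23.1%.

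**Step 3. Illustrations.** The documents give no removal or intolerance rate, so every rate here is assumed. Intolerance is treated as yes/no for simplicity, although the plan uses ordinal items.

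- All three allowed losses in one wear-home arm are subjects who removed needles for pain, with no other intolerant subject in that arm: the true rate is 3/13 = 23%, and the analysed rate is (3 - 3)/(13 - 3) = 0/10 = 0%.
- Intolerance is 4/13 = 31% in every arm, three intolerant subjects are dropped from each wear-home arm, and none from the long arm: ASP and Pyonex each show (4 - 3)/(13 - 3) = 1/10 = 10%, against 4/13 = 31% for long needles, with no true difference.

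**Step 4. General form.** Let p be the true share intolerant and q the share of those subjects who are dropped, with nobody else lost. The observed share is p(1 - q)/(1 - pq).

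| p | q | Calculation | Observed | Expected losses, 13pq |
|---|---|---|---|---|
| 0.30 | 0 | 0.30/1 | 30% | 0 |
| 0.30 | 0.25 | 0.225/0.925 | 24% | 1.0 |
| 0.30 | 0.50 | 0.150/0.850 | 18% | 2.0 |
| 0.30 | 0.75 | 0.075/0.775 | 10% | 2.9 |
| 0.30 | 1 | 0/0.70 | 0% | 3.9 |
| 0.10 | 0.50 | 0.050/0.950 | 5% | 0.7 |
| 0.50 | 0.50 | 0.250/0.750 | 33% | 3.3 |

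At p = 0.30, losses for q up to 0.75 stay within the three per arm already planned for, so the attrition count alone would not reveal them.

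**Step 5. Does the planned check help?** Comparing the characteristics of retained and dropped subjects may show that the groups differ. It cannot restore tolerance answers that were discarded or never collected.

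**The case against.** The strongest reply is that the link between removal and withdrawal is not in the protocol. Section 10.1 describes how long needles are expected to stay in; it does not tell subjects to leave them alone or call removal non-compliance. The consent pages are not part of the material available here, so any instruction in them cannot be judged. Withdrawal is optional. The 24-hour and 7-day contacts do not depend on a needle still being in place and can be done by telephone or online. A subject who removes a needle and completes every questionnaire therefore stays in the analysis with the discomfort recorded. Under 14.2, the stated response to a side effect is referral to an investigator, not withdrawal. All of this stands, and it is why the point concerns an open route and not a planned procedure.

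A reader might also infer that the problem is confined to two arms. That is true only of unsupervised removal at home. The clause in 13.6 covers all three arms, and a long-needle subject who cannot bear the needles may also leave and be excluded under 11.1.

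Finally, tolerance is measured by questionnaire and not by removal. The questionnaire itself is not in the documents, so it may already ask about removal. The fix allows for that.

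None of this answers the complete-case rule, which discards answers already given whatever the reason for the gap.

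**Conclusion.** The concern holds as a gap in the plan. An undefined, discretionary withdrawal ground applied by unblinded staff, followed by exclusion of any subject with missing data, can produce outcome-related losses whose likelihood differs by arm.

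Three stronger readings are tempting, and the documents do not support them:

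- **That early removers will be withdrawn.** The text only permits withdrawal, and does not name removal as a ground.
- **That the trial thereby loses the intolerance it sets out to measure.** Only the answers of subjects actually withdrawn would be lost.
- **That the bias favors hypothesis 2 as a whole.** Such losses could flatter both ASP and Pyonex against long needles, but hypothesis 2 also needs Pyonex to do better than ASP, and no direction is shown for that comparison.

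The size cannot be computed from the documents. At an assumed true intolerance of 30%, the observed figure runs from 30% (no intolerant subject dropped) to 0% (all dropped). These figures rest on the assumed rates and on no other losses occurring. With about 10 subjects analysed per arm, two or three such losses could change the tolerance comparison. The change is worth making before enrollment because it is cheap and protects one of the two outcomes.

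**What to change.** 1. **13.6:** add a sentence saying that early removal of a needle, by the subject or by staff, does not by itself end study participation or data collection, and that these subjects stay in their randomized group and still receive the 24-hour and 7-day contacts.
2. **11.1:** replace exclusion of subjects with missing data by analysis of the DVPRS and tolerance data that each randomized subject gave, with the number contributing at each time reported by arm. Keep the comparison of retained and dropped subjects as a description.
3. **Contacts:** unless the tolerance questionnaire already asks it, record in every arm whether the needles are out, when they came out, and why (fell out, removed by staff as scheduled, removed for discomfort, other). Report removal for discomfort by arm as a tolerance result.

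The other withdrawal grounds in 13.6, and the clinical decision on when a needle comes out, stay as they are.

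The cost is a sentence in 13.6, a revised rule in 11.1 and at most one added question on contacts already scheduled. The downside is that some subjects will be analysed after a short needle exposure, which the removal record will make visible. Analysing available data keeps the answers already given; only continued follow-up can supply the later ones, so items 1 and 2 are both needed.

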## **14.0** **Risks and Benefits**

### **14.1** **Risks of Harm:**

Identify all research-related risks of harm to which the subject will be exposed for each research procedure or intervention as a result of participation in this study. Consider the risks of breach of confidentiality, psychological, legal, social, and economic risks as well as physical risks. Do not describe risks from standard care procedures; only describe risks from procedures done for research purposes

The potential risks to participate in this study are minimal. There is a risk of accidental breach of confidentiality. Other risks associated with participating in this research study include:

**ACUPUNCTURE:**

**LIKELY:** *Likely and not serious:*

- Pain
- Bleeding
- Flare of signs and symptoms

**LESS LIKELY:** *Less Likely and not serious:*

- Infection

### **14.2** **Measures to Minimize Risks of Harm (Precautions, safeguards):**

For each research procedure or intervention, describe all measures to minimize and/or eliminate risk of harms to subjects and study personnel

Safeguards are in place for protecting subjects and their health data. The research consents and HIPAA Authorization Documents will be stored in a locked cabinet in a locked room. Subjects do not have to participate or answer any question that they do not want to complete. If at any time the patient reports a side effect, they will be referred to one of the Investigators for care.

Women of child bearing potential will be reminded that they only reliable methods of birth control are total abstinence or surgical removal of the uterus. Other methods, such as the use of condoms, a diaphragm or cervical cap, birth control pills, intrauterine device (IUD), or sperm-killing products are not totally effective in preventing pregnancy. They will be asked to alert study staff if they become pregnant or feel that they might be pregnant.

### **14.3** **Confidentiality Protections (for research records, data and/or specimens):**

Describe in detail the plan to maintain confidentiality of the research data, specimens, and records throughout the study and at its conclusion (e.g., destruction, long term storage, or banking). Explain the plan for securing the data (e.g., use of passwords, encryption, secure servers, firewalls, and other appropriate methods). If data will be shared electronically with other team members/collaborators outside the institution, describe the method of transmission and safeguards to maintain confidentiality. Explain whether this study may collect information that State or Federal law requires to be reported to other officials or ethically requires action, e.g., child or spouse abuse

**Safeguards for Protecting Information:** The research consents and HIPAA Authorization Documents will be stored in a locked cabinet in a locked room with restricted access. All identifiable research data including patient demographics will be kept in an electronic database separate from the coded research data, which will be encrypted, double password protected and the access will be restricted. Based on AFI 33-332, "The Air Force Privacy and Civil Liberties Program" and the National Institute of Standards and Technology Special Publication (NIST SP 800-88) which outlines the approved methods to destroy PII: The research data will be coded and any links to identifiable data (i.e., Master Key) will be destroyed as soon as all data mergers have occurred or no later than at the closure of the study. The anonymized research data will not be utilized for further research activity beyond the protocol stipulations without additional IRB approval. At the conclusion of the study, the data will be de-identified prior to review and analysis. Paper data, including completed consent forms: The research consents and HIPAA Authorization Documents will be stored in a locked cabinet in a locked room with restricted access.

**Electronic data:** Medical records will be annotated with ICD-10 code Z00.6 to reflect the subjects' participation in a research study, in which they are receiving a research-related treatment intervention. All research data that includes the Master Key of identifiable patient demographics and PHI/PII will be kept in an electronic database, separate from the coded research data, which will be encrypted, password protected and the access will be restricted.

**Long-term storage (following completion of the study and inactivation of IRB approval):** The research data will be coded and any links to identifiable data will be destroyed (in approved shredding bin) as soon as possible or no later than at the closure of the study, with the exception of those study subjects that consent to place their de-identified research data into the "Nellis Acupuncture Data Repository" (FWH20140048H) for future research. The anonymized research data will not be utilized for further research activity beyond the protocol stipulations without additional IRB approval. All de-identified research data will be maintained for 3 years following study closure. HIPAA forms will be maintained in hardcopy format for a minimum of 6 years. Following research study closure, the Long Term Storage Plan will be followed.

